## 3. Research scheme and technical route

### 3.1 Research Design

The principal investigator (PI) and project leader of this study are [name], chief physician of pediatrics of the Guangzhou Women and Children's Medical Center. In this study, a retrospective analysis was conducted on 220 enrolled neonates with necrotizing enterocolitis (NEC), with data collected from July 1, 2017 to December 31, 2022. Statistical methods including correlation analysis, multivariate logistic regression, mediation analysis, and receiver operating characteristic (ROC) curve analysis were employed to perform mutual analysis of the collected clinical data, laboratory parameters, and prognostic/mortality outcomes. This analysis aimed to identify meaningful biomarkers and establish a predictive model, thereby providing evidence for the pathophysiological mechanisms underlying NEC progression. It is anticipated that this will optimize clinical decision-making for NEC patients and improve the survival rate and quality of life of these neonates.

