### 3.2 Sample size

220 newborns who suffered from necrotizing enterocolitis between July 1, 2017 to December 31, 2022.

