### 3.6 Observation items

- (1). Baseline Characteristics: Neonatal demographics (sex, gestational age, birth weight, small for gestational age [SGA] status), maternal factors (mode of delivery, premature rupture of membranes, chorioamnionitis), neonatal birth history (1-min Apgar score  $\leq 7$ , intrauterine distress), and preterm complications (patent ductus arteriosus [PDA], respiratory distress syndrome [RDS], sepsis, shock), feeding pattern, and requirement for mechanical ventilation.

- (2). Laboratory and Clinical Assessment Indicators: Hepatobiliary function:

Albumin, albumin/globulin ratio, total bile acid; Hematologic and inflammatory parameters: White blood cell (WBC), absolute neutrophil (NEU), lymphocyte (LYM), monocyte (MON), eosinophil (EOS) counts, red blood cell (RBC), platelet (PLT) count, mean platelet volume (MPV), platelet distribution width (PDW), C-reactive protein (CRP), neutrophil-to-lymphocyte ratio (NLR), monocyte-to-lymphocyte ratio (MLR), neutrophil-to-monocyte ratio (NMR), systemic inflammatory index (SII), systemic inflammatory response index (SIRI), aggregate inflammatory systemic index (AISI); Metabolic: Serum lactate, blood glucose; Organ dysfunction assessment: Neonatal Sequential Organ Failure Assessment (nSOFA) score.

(3). Primary Outcome Indicators:

- Occurrence of perforated necrotizing enterocolitis (PNEC);
- In-hospital mortality.

(4). Secondary Outcome Indicators:

- Bell's staging of NEC;
- surgical NEC

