### 3.7 Statistical processing

Statistical analyses and graphic visualization were performed using SPSS 26.0 (IBM Corp.) and GraphPad Prism 9.0. Data for normally distributed, skewed distributed, and categorical variables were expressed as mean  $\pm$  standard deviation, median (interquartile range), and frequency (%), respectively. Intergroup comparisons of categorical variables were conducted using the Chi-square ( $\chi^2$ ) test or Fisher's exact test, while continuous variables were analyzed using the Student's t-test or Mann-Whitney U test. Variables with  $p < 0.05$  in univariate analysis were subsequently included in multivariate logistic regression analysis.

Mediation analysis was performed using the PROCESS macro 4.1, with 1000 bootstrap iterations to decompose the total effect into direct and indirect paths. Receiver operating characteristic (ROC) curve analysis was conducted using SPSS 26.0 to evaluate the predictive performance of individual and combined biomarkers. All analyses adopted two-tailed tests, and  $p < 0.05$  was considered statistically

significant.

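### The predictive model is judged by ROC alone; if it comes from the univariate screen and its risks are reported, those risks are likely to be too extreme, and no AUC can show it.

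*Combined protocol and SAP*

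**What the plan says.** - **Aim.** Section 3.1: "This analysis aimed to identify meaningful biomarkers and establish a predictive model". The same section goes on: "It is anticipated that this will optimize clinical decision-making for NEC patients".
- **Sample.** Section 3.2 gives a count of cases and no rationale for model size: "220 newborns who suffered from necrotizing enterocolitis between July 1, 2017 to December 31, 2022".
- **Candidates.** Section 3.6 lists a baseline block, opening with "Neonatal demographics (sex, gestational age, birth weight, small for gestational age [SGA] status", and a laboratory and clinical block, opening with "Albumin, albumin/globulin ratio, total bile acid; Hematologic and inflammatory parameters: White blood cell (WBC". Section 3.7 does not restrict which of these are screened.
- **Model building.** Section 3.7: variables with p < 0.05 "in univariate analysis were subsequently included in multivariate logistic regression analysis". No penalty or shrinkage is named.
- **Performance.** Section 3.7: "Receiver operating characteristic (ROC) curve analysis was conducted using SPSS 26.0 to evaluate the predictive performance of individual and combined biomarkers". The statistical row of the Abstract says the same.
- **Bootstrap.** It appears once, for the mediation analysis: "with 1000 bootstrap iterations to decompose the total effect into direct and indirect paths".

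Neither the Abstract nor sections 3.1 to 3.7 mention a calibration slope, intercept or plot, a Brier score, or internal or external validation.

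**The concern.** A model meant to inform decisions has to do two things: rank infants correctly, and attach the right probability to each rank. ROC analysis addresses only the first. A model that gives an infant 80% and one that gives the same infant 55% have the same AUC if they order the infants identically, and correcting the AUC for optimism does not change that.

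The second property is the one this procedure puts at risk. Screening many candidates in few infants, then fitting by maximum likelihood on the same data, inflates the coefficients. In new infants, high predicted risks then tend to be too high and low ones too low. At stake is the credibility of any risk, score or formula published from the model, since nothing in section 3.7 could reveal the distortion.

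**Working it through.** **1. Candidate count (section 3.6).**
- Baseline: 4 demographic + 3 maternal + 2 birth-history + 4 preterm complications + feeding pattern + mechanical ventilation = 15.
- Laboratory and clinical: 3 hepatobiliary + 16 hematologic and inflammatory + 2 metabolic + nSOFA = 22.
- Total 15 + 22 = 37, or 31 without the six derived ratios and indices.

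**2. Events per candidate.** Event numbers are not stated, so the share is assumed. At 10%: 22/37 = 0.6. At 30%: 66/37 = 1.8. At 50%: 110/37 = 3.0.

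**3. Analytic check.** For a logistic model with P candidate parameters and target shrinkage S, N = P / [(S − 1) ln(1 − R²/S)], where R² (Cox-Snell) = Nagelkerke R² × its maximum.
- Example, 20% events and Nagelkerke R² 0.30: maximum = 1 − exp{2[0.2 ln 0.2 + 0.8 ln 0.8]} = 0.632, so R² = 0.190. With P = 37 and S = 0.9, N = 37 / (0.1 × 0.2367) = about 1,563. Solving instead for S at N = 220 gives 0.58.
- Over event shares of 10–50% and Nagelkerke R² of 0.15–0.50 (all assumed), 37 candidates need about 690 to 4,460 infants for S = 0.9. At 220 the expected S is 0.33 to 0.76.
- Solved for P at N = 220 and S = 0.9: 2.2 parameters (15% events, Nagelkerke 0.15) to 10.3 (50% events, Nagelkerke 0.45).

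**4. Simulation of the procedure.** Assumptions: 220 infants, 37 normal predictors in blocks of 15 and 22, between-block correlation 0.1, t-test screen at p < 0.05, plain logistic fit, scoring in 20,000 new infants, 300 repeats per cell. Median calibration slope:

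| Event share | 6 true markers, log OR 0.4, within-block r 0.1 | 6, 0.4, r 0.3 | 4, 0.5, r 0.1 | 6, 0.6, r 0.3 |
|---|---|---|---|---|
| 15% | 0.58 | 0.49 | 0.59 | 0.40 |
| 25% | 0.65 | 0.52 | 0.68 | 0.46 |
| 40% | 0.68 | 0.59 | 0.73 | 0.52 |

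The slope was below 0.9 in 89–99% of repeats. On average 8 to 34 variables entered the model. Mean AUC was 0.79–0.93 in the fitting data and 0.72–0.82 in new infants.

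**5. Other assumptions.**
- Three true and 34 unrelated markers, event rates 15/25/35%: slopes 0.49/0.61/0.65 at log OR 0.3 and 0.68/0.75/0.81 at log OR 0.5. A pre-specified three-marker model gave 0.79–0.95. The predictor correlation for this set is not recorded.
- Events 15–50%, correlation 0 or 0.3: slopes 0.27–0.69.
- Independent predictors, three true markers: slopes as low as 0.22, with the three-marker model at 0.73–0.91.

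**6. What a slope means for one risk.** True risk = expit{m + slope × [logit(0.8) − m]}. At 25% events m = logit(0.25) = −1.099, and logit(0.8) − m = 1.386 + 1.099 = 2.485.
- Slope 0.61: −1.099 + 1.516 = 0.417, giving 60%.
- Slope 0.75: −1.099 + 1.864 = 0.765, giving 68%.

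**7. AUC does not react.** One fitted model, with its linear predictor multiplied by 0.5, 1 and 2, had AUC 0.828 each time. Its calibration slope was 1.05, 0.52 and 0.26, and its Brier score 0.166, 0.176 and 0.200.

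**The case against.** The strongest reply is that the plan asks a discrimination question. Section 2 seeks indicators that may predict progression and death, section 1.2 speaks of exploring predictive value, and nothing mentions a nomogram, score, calculator or individual probability. The clinical benefit in section 3.1 is an expectation, not a commitment. This stands in part. A reader might infer that the plan will deliver wrong individual risks, but the documents do not say that any risks will be published. Section 3.1 nevertheless names a predictive model as an aim and does not confine it to ranking, so the point holds conditionally.

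Second, the combined biomarkers need not be the screened model. Section 1.2 describes the combination as lactate, CBC and nSOFA, section 3.6 calls its lists observation items, and section 3.7 never links the two steps. If the combination is a small set fixed in advance, the nearer figure is the three-marker slope of about 0.8 to 0.95, a much milder problem. This also stands, unless the CBC markers are themselves picked by the screen.

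Third, the absence of a penalty is inferred from plain logistic regression in SPSS. That is the ordinary reading, but it is an inference.

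Fourth, the size is uncertain. A reader might pair the extreme slopes 0.49 and 0.81 with 25% events and quote a true risk of 53% to 71%. Those slopes belong to event rates of 15% and 35%, so the pairing is not valid. Event shares could also lie outside the simulated ranges, because section 3.4 limits inclusion to surgically treated infants and perforation may be common among them.

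**Conclusion.** The concern holds in conditional form. Section 3.7 has no measure that could detect miscalibration, and the model-building route it describes is one that tends to produce it. If the combined model comes from the screen and its coefficients or predicted risks are reported, risks that are too extreme are the expected result. That is an expectation on average, not a certainty for this one dataset.

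The direction was the same under every assumption tried. The size is illustrative only, because it rests on assumed event rates, signal strengths, normal predictors and correlations, and the near-collinearity of the derived indices was not modelled. The odds ratios and AUCs can still be produced. What is unsupported is any statement about an individual infant's risk. The plan should be changed, but this does not invalidate the study.

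**What to change.** In section 3.7, for PNEC and for in-hospital mortality separately:

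1. State which model the combined biomarkers are.
2. Report the bootstrap optimism-corrected calibration slope and calibration-in-the-large beside the optimism-corrected AUC. Repeat the whole model-building procedure, including any univariate screen, in each resample. A calibration check on the same 220 infants will not do, because a maximum-likelihood logistic model has slope 1 in its own data by construction.
3. Before any predicted risk is reported, multiply the coefficients by the corrected slope and re-estimate the intercept. The alternative is a pre-specified ridge model on a small pre-specified lactate, CBC and nSOFA set, with its size fixed from the observed event count. A fixed cap chosen now is not safe, since the supportable number ranges from about 2 to 10.
4. If this is not done, limit the conclusion to discrimination and make no claim about individual risk.

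No new patients or data are needed. The cost is SAP wording, a short script outside the SPSS menus, less extreme predicted risks and a more modest headline.

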Statistical processing	Statistical analyses and graphic visualization were performed using SPSS 26.0 (IBM Corp.) and GraphPad Prism 9.0. Data for normally distributed, skewed distributed, and categorical variables were expressed as mean $\pm$ standard deviation, median (interquartile range), and frequency (%), respectively. Intergroup comparisons of categorical variables were conducted using the Chi-square ( $\chi^2$ ) test or Fisher's exact test, while continuous variables were analyzed using the Student's t-test or Mann-Whitney U test. Variables with $p < 0.05$ in univariate analysis were subsequently included in multivariate logistic regression analysis.  Mediation analysis was performed using the PROCESS macro 4.1, with 1000 bootstrap iterations to decompose the total effect into direct and indirect paths. Receiver operating characteristic (ROC) curve analysis was conducted using SPSS 26.0 to evaluate the predictive performance of individual and combined biomarkers. All analyses adopted two-tailed tests, and $p < 0.05$ was considered statistically significant.
Abbreviation	NEC, necrotizing enterocolitis; PNEC, perforated necrotizing

enterocolitis; VLBW, very low birth weight; SGA, small for gestational age; NICUs, neonatal intensive care units; PDA, patent ductus arteriosus; RDS, Respiratory distress syndrome; CRP, C-reactive protein; WBC, white blood cell; CBC, complete blood count; NEU, absolute neutrophil count; LYM, absolute lymphocyte count; MON, absolute monocyte count; EOS, eosinophilic granulocyte; RBC: red blood cell; PLT, platelet count; MPV, mean platelet volume; PDW, platelet distribution width; NLR, neutrophil-to-lymphocyte ratio; NMR, neutrophil-to-monocyte ratio; MLR, monocyte-to-lymphocyte ratio; SII, systemic inflammatory index =  $(NEU*PLT)/LYM$ ; SIRI, systemic inflammatory response index =  $(NEU*MON)/LYM$ ; AISI, aggregate inflammatory systemic index =  $(NEU*MON*PLT)/LYM$ ; nSOFA, neonatal sequential organ failure assessment; ROC, receiver operating characteristic; AUC, the area under the ROC curve; OR, odds ratio; CIs, confidence intervals.

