## 1.2 Creativity

To address these gaps, the present retrospective cohort study aims to explore the potential predictive value of integrating metabolic (lactate), hematologic (CBC), and organ dysfunction (nSOFA) metrics for NEC and its associated mortality in preterm infants. By combining these complementary markers, we aim to overcome the

limitations of single biomarkers and fill the knowledge gap regarding risk stratification for perforated NEC—an outcome that holds profound implications for clinical decision-making and improving the survival rate of preterm infants.

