## 2. Research objective

This retrospective cohort study aims to enroll patients with necrotizing enterocolitis (NEC) from July 1, 2017 to December 31, 2022, conduct a comprehensive analysis of their clinical characteristics, metabolic indicators, laboratory parameters, prognosis, and outcomes, and identify indicators that may predict the progression of neonatal NEC and its associated mortality.

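### Section 1.2 justifies combining lactate, CBC and nSOFA by a gain over single markers, but section 3.7 gives no method for estimating or testing that gain

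*Combined protocol and SAP*

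**What the plan says.** Section 1.2 (Creativity) states the study's contribution as "integrating metabolic (lactate), hematologic (CBC), and organ dysfunction (nSOFA) metrics" to predict NEC and related death in preterm infants. It continues: "By combining these complementary markers, we aim to overcome the" and then "limitations of single biomarkers and fill the knowledge gap regarding risk stratification for perforated NEC". That is a statement about a combination relative to its parts.

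The formal objective in section 2 is looser: to "identify indicators that may predict the progression of neonatal NEC and its associated mortality". Section 3.6 names two primary outcomes, PNEC and in-hospital death.

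On method, section 3.7 says ROC analysis will be run in SPSS "to evaluate the predictive performance of individual and combined biomarkers". The Statistical processing row of the Abstract repeats this. Section 3.7 also says that variables below the 0.05 threshold "in univariate analysis were subsequently included in multivariate logistic regression analysis". The only general rule is "two-tailed tests, and $p < 0.05$ was considered statistically significant". Section 3.2 gives the sample as "220 newborns who suffered from necrotizing enterocolitis between July 1, 2017 to December 31, 2022", with no derivation.

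**The concern.** Every infant contributes to every ROC curve, so the AUC of a single marker and the AUC of a combination containing it are positively correlated. The uncertainty of their difference depends on that correlation and cannot be recovered from two separate intervals. No section names a paired AUC comparison, an interval for an AUC difference, a nested-model test or a decision rule. The listed chi-square, Fisher, t and Mann-Whitney tests compare groups of infants, not AUCs.

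Without a method, a reader of the results has two informal routes. Taking the larger AUC as the winner favours the combination even when the added markers carry nothing. Treating the AUCs as independent, or looking for non-overlapping intervals, can miss a moderate real gain.

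This is separate from optimism in the combined AUC. Correcting optimism moves the point estimate, but the difference still needs its own standard error.

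**Working it through.** **Inputs.** From the documents: N = 220 (section 3.2) and two-sided 0.05 (Abstract and section 3.7). Everything else is assumed, because the documents give no event count, AUC or correlation. There is no planned power or precision figure to reproduce.

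**1. By hand, across event counts.** Assume AUCs of 0.75 (single) and 0.82 (combined). With n1 events and n0 non-events, the Hanley-McNeil formula is

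SE² = [A(1−A) + (n1−1)(Q1−A²) + (n0−1)(Q2−A²)] / (n1·n0), where Q1 = A/(2−A) and Q2 = 2A²/(1+A).

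For A = 0.75 with 66 events: [0.1875 + 65×0.0375 + 153×0.0804] / 10,164 = 0.001468, so SE = 0.0383. For A = 0.82, SE = 0.0341. The separate 95% intervals are 0.675 to 0.825 and 0.753 to 0.887, which overlap.

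SE of the difference = √(SE1² + SE2² − 2r·SE1·SE2), where r is the correlation between the two AUC estimates:
- r = 0 (pairing ignored): √(0.001467 + 0.001163) = 0.051; z = 0.07/0.051 = 1.37; p = 0.17
- r = 0.5: SE 0.036; p = 0.054
- r = 0.7: SE 0.028; p = 0.013

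| Events of 220 | SE, r = 0 | p | SE, r = 0.7 | p |
|---|---|---|---|---|
| 22 | 0.084 | 0.40 | 0.046 | 0.13 |
| 44 | 0.061 | 0.25 | 0.034 | 0.037 |
| 66 | 0.051 | 0.17 | 0.028 | 0.013 |
| 110 | 0.044 | 0.11 | 0.024 | 0.004 |

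The same two AUCs lead to different conclusions depending on whether the pairing is used. At 22 events even the paired comparison is inconclusive.

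**2. Power by simulation.** Correlated binormal markers, 44 events and 176 non-events, true AUCs 0.75 and 0.83, DeLong standard errors.

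| Marker correlation | Paired SE | Unpaired SE | Power, paired | Power, unpaired | Intervals do not overlap |
|---|---|---|---|---|---|
| 0.5 | 0.039 | 0.053 | about 52% | about 27% | about 6% |
| 0.7 | 0.032 | 0.053 | about 72% | about 24% | about 2% |

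Arithmetic check at 0.7. Paired: Φ(0.08/0.032 − 1.96) = Φ(0.54) = 0.71. Unpaired: the difference still varies with SE 0.032 but is judged against 1.96×0.053 = 0.104, so Φ((0.08 − 0.104)/0.032) = Φ(−0.75) = 0.23. Both agree with the simulation.

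**3. Larger gains.** With the same 44/176 split and marker correlation 0.7, true AUCs of 0.70 and 0.88 give non-overlapping intervals in about 88% of cohorts, and 0.65 and 0.85 in about 91%.

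**4. Ranking by point estimate.** One real marker (AUC 0.75) plus two pure-noise markers in a fixed logistic model, 44 events in 220: the combined apparent AUC is higher in about 85% of cohorts, while the likelihood-ratio test on the two added terms rejects in about 6%. Over 22 to 110 events and two to four noise markers, the share with a higher AUC is 82% to 97% and the mean apparent gain is 0.006 to 0.025. DeLong applied to these nested models rejected in 0% to 3.5% of runs. It is conservative there, which is a reason to prefer the likelihood-ratio test for nested comparisons.

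**5. Effect of the planned screen.** If noise candidates must first pass univariate p < 0.05 on the same infants, the likelihood-ratio test on the survivors rejects in about 29%, 41% and 49% of null cohorts with 10, 16 and 20 independent candidates. Section 3.6 lists 16 haematologic and inflammatory indices (WBC through AISI, including CRP). Independence is an assumption, and several of these indices share components.

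**The case against.** **The comparison is not the stated objective.** Section 2 asks only for predictive indicators, and section 3.1 for biomarkers and a predictive model. No section states a superiority hypothesis. A reader might infer that combined versus single is the study's central question, but the documents support only that section 1.2 gives it as the rationale. This part of the objection stands.

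**The plan sets no bad rule.** A reader might infer that results will be judged from separate AUCs or from interval overlap. Section 3.7 states neither rule; it is silent. The planned logistic regression would also give adjusted p-values for each marker, which bear on added value. But the plan does not assign that model to this comparison, and its terms come from a screen on the same data. An analyst could add a paired test later, but would then choose comparator and outcome after seeing results.

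**The noise figure depends on how the combination is built.** The 85% assumes a fixed combination. With two noise candidates passed through the p < 0.05 screen instead, noise enters, and the combined AUC is higher, in only about 9% of cohorts. This stands, and the figure is used here only for a fixed combination.

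**A formal test alone would not repair the plan.** This also stands. On screened terms a likelihood-ratio p-value is badly inflated (step 5), so the remedy must deal with selection.

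**Conclusion.** The omission is confirmed: the plan offers the combination as an improvement on single markers and provides no method for the improvement. For a moderate gain the consequence is material. Under the assumptions in step 2, ignoring the pairing inflates the standard error of the difference by 0.053/0.039 = 1.4 to 0.053/0.032 = 1.7 times and cuts power by half or more. These figures rest on assumed events, AUCs and correlations.

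It would be too strong to say that interval overlap nearly always hides a gain. That holds for moderate gains and fails for large ones (step 3). The plan should be changed on this point, but the gap does not undermine the study's broader aim of identifying predictors.

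**What to change.** Add to section 3.7:

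> For each primary outcome (PNEC, in-hospital death) the combined model is prespecified as lactate, nSOFA and a named CBC index, entered without the univariate p<0.05 screen. Its added value over nSOFA alone and over lactate alone is tested by the likelihood-ratio test in nested logistic models. The optimism-corrected AUC difference is reported with a paired bootstrap 95% CI that resamples infants and refits the models. Single markers are compared with each other by the paired DeLong test. If CBC terms are instead chosen from the data, the selection is repeated in every bootstrap sample and no likelihood-ratio p-value is reported for the selected terms.

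Any statement that the combination is better should rest on these results. The CBC index must be named before its relation to the outcomes is examined; otherwise the last sentence of the insert applies.

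The cost is one paragraph and a modest amount of extra analysis on data already being collected. The downside for the sponsor is that a claimed gain may prove smaller or non-significant. With few events (22 in the table above) even the paired analysis may be inconclusive.

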## 1. project basis

### 1.1 Research background

Necrotizing enterocolitis (NEC), a life-threatening gastrointestinal disorder predominantly, affects 5–12% of very low birth weight (VLBW) neonates, with 20–40% of cases progressing to severe disease requiring surgical intervention, while survivors often endure lifelong consequences, including short-bowel syndrome and neurodevelopmental impairments [1-4]. Despite advances in neonatal care, early identification of high-risk patients remains challenging due to the nonspecificity of clinical signs (e.g., abdominal distension, feeding intolerance) and radiographic findings (e.g., pneumatosis intestinalis), which frequently manifest only after irreversible bowel damage has occurred [5]. Furthermore, current diagnostic tools or conventional biomarkers lack both sensitivity and specificity for early risk stratification of NEC, underscoring an urgent need for biomarkers that integrate pathophysiological mechanisms to guide preemptive therapeutic strategies.

Emerging evidence underscores the multifactorial pathophysiology of NEC, where intestinal ischemia-reperfusion injury, exaggerated immune activation, and microbial dysbiosis converge to drive disease progression [6]. Hypoxic-ischemic injury constitutes a key pathological mechanism underlying intestinal mucosal damage in NEC, driving dysregulation of cellular processes including apoptosis, autophagy, proliferation, and migration within intestinal tissues [7]. In infants with NEC, persistent hypoxemia and compromised tissue perfusion induce metabolic reprogramming, marked by a shift toward glycolytic dominance—a compensatory adaptation to oxygen deprivation. Within this framework, serum lactate, as a well-established marker of tissue hypoperfusion and anaerobic metabolism, has garnered attention for its prognostic relevance. Elevated lactate levels correlate with transmural intestinal necrosis and predict fatal outcomes in NEC, reflecting the severity of ischemic insult [8,9]. However, lactate alone lacks specificity, as hyperlactatemia may arise from concurrent sepsis or perinatal asphyxia, limiting its standalone utility [10,11]. Recent studies propose combining lactate with

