### 3.3 data collection

Data collection was performed via structured extraction from electronic medical

records. The following variables were systematically retrieved: (1) Neonatal medical history, including sex, gestational age, birth weight, and history of birth asphyxia (e.g., Apgar scores); (2) Maternal medical history, particularly mode of delivery, chorioamnionitis, and premature rupture of membranes; (3) NEC-related clinical parameters: Bell's staging, clinical manifestations (abdominal distension, bloody stools, pneumoperitoneum), complications (patent ductus arteriosus [PDA], sepsis, shock), therapeutic interventions (mechanical ventilation, surgical treatment), and mortality; (4) CBC parameters, lactate levels, and parameters required for calculating the nSOFA score at the onset of NEC.

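### The ROC analysis in section 3.7 has no clinical base model and no added-value test, so the gain in discrimination from lactate, CBC and nSOFA over already known information is not measured

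*Combined protocol and SAP*

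**What the plan says.** Two motives are given. Section 1.1 states that "early identification of high-risk patients remains challenging due to the nonspecificity of clinical signs". Section 1.2 speaks of overcoming the "limitations of single biomarkers and fill the knowledge gap regarding risk stratification for perforated NEC". Section 3.1 intends a predictive model, hopes that it will help clinical decisions, and says the methods will "perform mutual analysis of the collected clinical data, laboratory parameters, and prognostic/mortality outcomes".

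Section 3.3 extracts "clinical manifestations (abdominal distension, bloody stools, pneumoperitoneum" among the NEC-related parameters. The observation items in section 3.6 include "Neonatal demographics (sex, gestational age, birth weight, small for gestational age [SGA] status", together with sepsis, shock, "feeding pattern, and requirement for mechanical ventilation". Abdominal distension, bloody stools and pneumoperitoneum are not on that list.

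In section 3.7, variables with p < 0.05 "in univariate analysis were subsequently included in multivariate logistic regression analysis". ROC analysis is then used "to evaluate the predictive performance of individual and combined biomarkers". The abstract repeats this text. Neither place names a clinical comparator model, a comparison of AUCs or any other measure of added value.

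**The concern.** A stand-alone AUC includes whatever the markers share with prematurity and with severity already visible at the bedside. Gestational age and birth weight are known before any sample is drawn. If lactate, CBC indices and nSOFA largely track them, a respectable AUC can coexist with little improvement in what a clinician could already predict.

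The ROC step sets combined markers beside single ones, which serves the motive in section 1.2. The motive in section 1.1, the weakness of clinical signs, has no matching analysis of discrimination. A good marker AUC could then be presented as support for the benefit to decisions anticipated in section 3.1, although that benefit was never measured.

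**Working it through.** **Step 1: what each planned analysis can deliver.**

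| Analysis in 3.7 | Clinical variables present? | Shows added discrimination? |
|---|---|---|
| Group comparisons | Yes, one at a time | No |
| Multivariate logistic regression | Only those with univariate p < 0.05 | No; shows independent association |
| ROC, single and combined markers | None named | No; no reference to compare with |

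**Step 2: status of the signs.** Distension and bloody stools are collected (3.3) but absent from the list in 3.6. Section 3.1 speaks of the collected clinical data, and the entry rule in 3.7 is not restricted to biomarkers or to the 3.6 items. The signs could therefore enter the regression; nothing says whether they will. On timing, the reference to NEC onset in 3.3 stands only in item (4), the laboratory and nSOFA data. The signs, in item (3), carry no time point.

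**Step 3: does a marker AUC determine the gain?** The documents give no AUC, correlation or event count, so every input here is an assumption. For binormal scores with within-group correlation r:

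- d = √2 · Φ⁻¹(AUC)
- D² = (d_c² + d_m² − 2·r·d_c·d_m) / (1 − r²), with c = clinical reference and m = markers
- combined AUC = Φ(√(D²/2))

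For AUC 0.75, d = 0.954 and d² = 0.910. With both scores at 0.75:

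- r = 0: D² = 0.910 + 0.910 = 1.820, AUC = Φ(0.954) = 0.83
- r = 0.8: D² = (1.820 − 1.6 × 0.910)/0.36 = 1.011, AUC = Φ(0.711) = 0.76

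| r | Gain, reference 0.75, markers 0.75 | Gain, reference 0.70, markers 0.75 |
|---|---|---|
| 0 | 0.08 | 0.10 |
| 0.3 | 0.05 | 0.07 |
| 0.5 | 0.03 | 0.06 |
| 0.7 | 0.02 | 0.05 |
| 0.8 | 0.01 | 0.05 |

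With a marker AUC of 0.70, the gain runs from 0.092 (reference 0.65, r = 0) to 0.000 (reference 0.75 with r = 0.78, or 0.80 with r = 0.62). The marker AUC alone does not fix the gain.

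**Step 4: could 220 infants support an added-value test?** The figure of 220 is a case count without power, effect size or event rate, so it cannot be reproduced. As an illustration, take the F test for additional information from one marker, two-sided 0.05, with c = n₁n₂/N and noncentrality c(D² − d_c²)/(1 + c·d_c²/(N − 2)). For reference 0.75, marker 0.70 and r = 0.3, D² = 1.138. At 44 events, c = 44 × 176/220 = 35.2 and the noncentrality is 35.2 × 0.228/1.147 = 7.0, so power is 0.75.

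| Assumed events of 220 | Power, gain 0.025 (r = 0.3) | Power, gain 0.011 (r = 0.5) | 95% half-width, single AUC 0.70 (Hanley-McNeil) |
|---|---|---|---|
| 44 (20%) | 0.75 | 0.39 | 0.093 |
| 66 (30%) | 0.84 | 0.47 | 0.079 |
| 110 (50%) | 0.89 | 0.53 | 0.069 |

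These powers are for one added marker. Testing several together uses more degrees of freedom and has less power for the same gain.

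**The case against.** The strongest reply has three parts.

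*The signs are not excluded.* A reader might infer from their absence in 3.6 that they never enter a comparison or model. The documents do not support that. No section limits the analysis to the 3.6 list, and 3.1 and the entry rule in 3.7 could admit them. What stands is that their role and timing are unspecified.

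*The regression is informative.* A reader might infer that the study cannot show that the markers add anything. That goes too far. Gestational age, birth weight, sepsis, shock and ventilation are all listed in 3.6 and enter if they pass the screen. A marker that stays significant beside them is evidence of association beyond prematurity and clinical severity. It is still not a gain in discrimination, and the screen may leave no clinical variable in the model.

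*The aims are modest.* Sections 1.2 and 2 are exploratory, the comparator named in 1.2 is the single biomarker, and better decisions are only anticipated in 3.1. It would be wrong to say that the study fails a stated aim of beating a bedside model, because it states none. The motive in 1.1 nevertheless remains without a matching analysis.

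The illustration also cuts both ways. With the reference at 0.70 and markers at 0.75, the gain is never below 0.05. A gain near zero needs a reference at least as good as the markers and substantial correlation between them. Distension and bloody stools may discriminate weakly, since section 3.4 uses them to confirm NEC and they may vary little in this cohort.

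**Conclusion.** The point holds in limited form. That 3.7 has no clinical base model and no added-value test rests on the text alone and needs no assumption. The regression can establish independent association, which is useful but is a different quantity from improved discrimination.

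The size is illustrative. Under the assumed binormal model, a marker AUC of 0.75 fits a gain of 0.08 or 0.01 when the reference is also 0.75, and 0.10 to 0.05 when it is 0.70. The conclusion does not depend on any one of these inputs, only on the fact that a stand-alone AUC does not identify added value. This does not invalidate the study. It is a worthwhile, inexpensive improvement.

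**What to change.** In section 3.7, for each primary outcome (PNEC and in-hospital mortality):

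1. Prespecify a reference model with gestational age and birth weight. Add abdominal distension and bloody stools only if they were recorded at NEC onset and vary in the cohort; state this in 3.3 and list them in 3.6. Leave out pneumoperitoneum, which is too close to the PNEC outcome.
2. Name a small marker set in advance: lactate, one named CBC index and nSOFA. Section 3.6(2) lists 22 candidates, and choosing among them by p < 0.05 in the same infants would flatter the increment. Ventilation and shock are best kept out of the reference, because section 1.1 says nSOFA already covers respiratory and cardiovascular function.
3. Add the markers in the same infants. Report the likelihood-ratio test and the bootstrap optimism-corrected change in AUC with its confidence interval.
4. Base any claim of added predictive value on that increment, and label stand-alone marker AUCs as descriptive.

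The cost is SAP wording and one nested comparison per outcome on variables already extracted, plus a check of when the signs were recorded. The model would carry 5 coefficients (2 + 3), or 7 with both signs (4 + 3), if each term is entered linearly. At an assumed 44 events that is 44/5 = 8.8 or 44/7 = 6.3 events per coefficient, so the event counts should be stated before the model is fixed. The headline figure may be less favourable than a stand-alone AUC.
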